5.5 Duration of Follow Up

Patients will be followed for 30 days after the last dose is administered or until one of the following occurs: patient enrolls on another protocol, patient receives standard of care, or death, whichever comes first. The follow-up will consist of a phone call between Days 27-30 after the last dose to evaluate adverse events that were ongoing and any new events that might be deemed related to the therapy. Toxicities felt to be possibly, probably, or definitely related to the study drugs that have not resolved or stabilized by Day 30 post-treatment will be followed until stabilization or resolution via phone calls as clinically indicated. Whenever possible, Phase II patients will be followed via phone calls until they progress or start another treatment for their cancer.

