7.2.2 Routine Adverse Event Reporting

All Adverse Events **must** be reported in routine study data submissions. **AEs reported through CTEP-AERS must also be reported in routine study data submissions.**

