7.2.3.2 Expedited Reporting Guidelines

Use the NCI protocol number and the protocol-specific patient ID assigned during trial registration on all reports.

Note: A death on study requires both routine and expedited reporting regardless of causality, unless as noted below. Attribution to treatment or other cause must be provided.

Death due to progressive disease should be reported as **Grade 5 “Disease Progression”** in the system organ class (SOC) ”General disorders and administration site conditions.” Evidence that the death was a manifestation of underlying disease (e.g., radiological changes suggesting tumor growth or progression; clinical deterioration associated with a disease process) should be submitted.

Expedited Reporting Requirements for Adverse Events that Occur on Studies under an IND/IDE within 30 Days of the Last Administration of the Investigational Agent/Intervention ^{1,2}

FDA REPORTING REQUIREMENTS FOR SERIOUS ADVERSE EVENTS (21 CFR Part 312)

NOTE: Investigators **MUST** immediately report to the sponsor (NCI) **ANY** Serious Adverse Events, whether or not they are considered related to the investigational agent(s)/intervention (21 CFR 312.64)

An adverse event is considered serious if it results in **ANY** of the following outcomes:

- 1) Death
- 2) A life-threatening adverse event
- 3) An adverse event that results in inpatient hospitalization or prolongation of existing hospitalization for \geq 24 hours
- 4) A persistent or significant incapacity or substantial disruption of the ability to conduct normal life functions
- 5) A congenital anomaly/birth defect.
- 6) Important Medical Events (IME) that may not result in death, be life threatening, or require hospitalization may be considered serious when, based upon medical judgment, they may jeopardize the patient or subject and may require medical or surgical intervention to prevent one of the outcomes listed in this definition. (FDA, 21 CFR 312.32; ICH E2A and ICH E6).

ALL SERIOUS adverse events that meet the above criteria **MUST** be immediately reported to the NCI via CTEP-AERS within the timeframes detailed in the table below.

Hospitalization	Grade 1 and Grade 2 Timeframes	Grade 3-5 Timeframes
Resulting in Hospitalization \geq 24 hrs	10 Calendar Days	24-Hour 5 Calendar Days
Not resulting in Hospitalization \geq 24 hrs	Not required	

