12.1 Data Reporting

12.1.1 Method

This study will be monitored by the Clinical Trials Monitoring Service (CTMS). Data will be collected in the Center for Cancer Research C3D database and will be transmitted to CTMS electronically at least once every 2 weeks.

Note: All adverse events that have occurred on the study, including those reported through CTEP-AERS, must be reported via the monitoring method identified above.

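### The post-treatment safety call in Section 5.5 is narrower in scope, and may come earlier, than the 30-day serious-event reporting duty in Section 7.2.3.2 requires

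*Combined protocol and SAP*

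**What the plan says.** **Section 5.5** sets the length of follow-up: "Patients will be followed for 30 days after the last dose is administered", with an earlier end if one of these occurs: "patient enrolls on another protocol, patient receives standard of care, or death, whichever comes first". The planned contact is stated as "The follow-up will consist of a phone call between Days 27-30 after the last dose", and its purpose is to "evaluate adverse events that were ongoing and any new events that might be deemed related to the therapy". After that, a relatedness condition governs continued follow-up: "Toxicities felt to be possibly, probably, or definitely related to the study drugs that have not resolved or stabilized by Day 30 post-treatment" are followed by phone until they resolve or stabilize. A last sentence adds phone calls to Phase II patients, where possible, until progression or new cancer treatment. It does not say what those calls ask about safety.

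**Section 7.2.3.2** covers events within 30 days of the last administration. It tells investigators to report any "Serious Adverse Events, whether or not they are considered related to the investigational agent(s)/intervention". Deaths on study need routine and expedited reports whatever the cause, with a stated way of coding deaths from progression. Its footnote 1 brings in an attribution condition (possible, probable or definite) only for serious events more than 30 days after the last dose.

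**Section 7.3.4** asks for deaths within 30 days of a research intervention to be sent to the Clinical Director, unless due to progressive disease.

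**Sections 7.2.2 and 12.1.1** say that all adverse events must "be reported in routine study data submissions" and that "All adverse events that have occurred on the study, including those reported through CTEP-AERS, must be reported". Neither gives an end date.

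**Section 10** marks an adverse event evaluation in the off-treatment column. The footnote calls it an off-study evaluation and gives no day and no scope.

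**The concern.** Section 7 says what must be reported once a site knows of it. Section 5.5 says what the site asks. If the question is narrower than the duty, a reportable event can go unnoticed without anyone departing from the protocol.

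The relatedness condition also sits on the wrong side of the protocol's own boundary. Section 7.2.3.2 reserves it for events after 30 days, whereas Section 5.5 applies it to new events inside the 30 days.

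Safety and tolerability is a primary objective (Section 1.1), and the trial is open-label with no control arm, so attribution is a judgement by the treating team. If that judgement decides what is asked, the sponsor cannot review it afterwards for events that were never elicited. The patients concerned are those whose follow-up runs its full course. Early ending of follow-up on new treatment is a separate clause with its own effect.

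**Working it through.** No sample size, power or error rate is involved. The check sets the passages side by side, with one subtraction for timing.

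**Scope within 30 days of the last dose**

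| New event after the last dose | Section 5.5 call asks? | Reporting duty if the site learns of it? |
|---|---|---|
| Serious, might be related | Yes | Yes (7.2.3.2) |
| Serious, judged unrelated | No | Yes (7.2.3.2) |
| Death, judged unrelated to treatment | Not stated | Yes (7.2.3.2; also 7.3.4 unless due to progression) |
| Non-serious, judged unrelated | No | All events reportable (7.2.2, 12.1.1), but no end date stated |

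The firm conflict is in the second and third rows. The fourth is weaker, because Section 7.2.2 does not say how long after the last dose non-serious events must be collected. The exceptions in the SPEER column and Section 7.2.3.3 lift expedited reporting for named events and grades. They do not limit what should be asked.

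**Timing**

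- Window in Section 7.2.3.2: 30 days after the last administration.
- Earliest compliant call in Section 5.5: Day 27.
- Uncovered: 30 − 27 = 3 days, and 3/30 = 10% of the window. A call on Day 30 leaves 30 − 30 = 0 full days.

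**Whether another contact closes the gap**

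- *Off-treatment column of the calendar.* It carries an adverse event evaluation with no attribution filter, but no day. Suppose, as an assumption, that it is held at the end of the last cycle. Dosing ends on day 5 of 28, so the visit falls 28 − 5 = 23 days after the last dose, which is 30 − 23 = 7 days short of the window. Read instead as an evaluation when the patient leaves the study, it could fall near Day 30. However, the column includes a physical examination, and Section 5.5 says follow-up consists of a phone call. The documents do not settle which reading applies.
- *Later Phase II calls.* These are made only where possible, end at progression or new treatment, and have no stated safety content.
- *Section 5.6.* It removes patients once the 30-day period is complete, but adds no contact.

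No other section guarantees an unfiltered question that covers the whole 30 days.

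**The case against.** The best case for the plan has four parts.

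- *The filter is loose.* Section 5.5 says new events that might be deemed related, and Section 7.2.1 defines a possible attribution as one that may be related. A cautious team would exclude little. This narrows the gap but does not close it, because an event judged unrelated is still outside the call.
- *The reporting duties stand.* Sections 7.2.2, 7.2.3.2, 7.3.4 and 12.1.1 bind for anything the site learns, and most staff would record whatever a patient mentions. That is right: the defect is in planned ascertainment, not in the reporting rule.
- *There are other contacts.* The calendar evaluation and the Phase II calls exist, so the Section 5.5 call should not be described as the only post-treatment contact. Neither has a defined day and safety scope.
- *Day 27 is the worst case of a scheduling window.* This is also true, and 3 days is therefore a maximum.

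A reader might also infer more than the documents support:

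- *That anemia or hepatic events would be lost.* Anemia and raised bilirubin are on the TRC102 risk list (Section 7.1), hemolytic anemia was the dose-limiting toxicity (Section 2.5), and hepatic injury after stopping temozolomide is described in Sections 2.3 and 7.1.1. Such events might readily be deemed related, so the call as worded would ask about them.
- *That Section 7 sets a 30-day window for all adverse events.* The explicit window belongs to the expedited rules.
- *That a planned serious-event count is biased.* Section 13 defines no such count, and the dose decision uses cycle 1 DLTs, which require relatedness by definition (Section 5.2).

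**Conclusion.** The point holds as a mismatch between Section 5.5 and Section 7.2.3.2. The call filters new events on attribution during a period when the protocol requires serious events and deaths to be reported without that filter, and it may be made up to 3 days before the period ends. No other section clearly makes up the difference.

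Its size can be stated only as a gap in what is asked: serious events and deaths judged unrelated at any time in the 30 days, and any new event in up to 3 of those days. The number of affected patients cannot be derived, because the documents give no rate of such events. No decision rule, power figure or MTD determination changes.

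The conclusion assumes that a site follows Section 5.5 as written and that the undated calendar evaluation is not reliably held at or after Day 30. The change is worth making because it serves a primary objective and costs very little.

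**What to change.** Reword the follow-up sentence in Section 5.5 in three respects:

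1. **Scope.** Have the call ask about all new adverse events since the last contact, whatever the attribution, and about vital status, through Day 30 after the last dose. At minimum it should cover all serious events and deaths.
2. **Timing.** Make the call on or shortly after Day 30, so that it looks back over the whole window.
3. **Relatedness.** Keep that condition only for follow-up beyond Day 30, where Section 5.5 and footnote 1 of Section 7.2.3.2 already use it.

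For consistency, give the off-treatment column in Section 10 a day and a scope, and state in Section 7.2.2 how long non-serious events are collected after the last dose.

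The cost is a short amendment and a few more events to record. The number of contacts does not change, and neither treatment nor patient management is affected.

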5.6 Criteria for Removal from Study

Patients will be removed from study for one of the following reasons: completed 30-day follow-up period or toxicities are unresolved but stabilized. The reason for study removal and the date the patient was removed must be documented in the medical record and communicated to Central Registration per [Section 4](#).

6. DOSING DELAYS/DOSE MODIFICATIONS

Non-hematologic toxicities (at least possibly related to therapy) should have resolved to \leq Grade 1 or baseline prior to starting the next cycle or receiving the next dose of TRC102 or TMZ within a cycle. Grade 2 electrolyte abnormalities, grade 2 nausea/vomiting/diarrhea in the absence of maximal palliative support, or any grade alopecia, will not result in holding or delaying study drugs.

Hematologic toxicities (at least possibly related to therapy) should have resolved to \leq Grade 1 for thrombocytopenia, \leq Grade 2 for neutropenia and anemia prior to resuming therapy except any grade lymphopenia, leucopenia in the absence of grade 3 neutropenia.

Even though study drug administration is allowed at these lower grades, every effort should be made to correct the abnormal lab values to normal if possible. If the potassium level is grade 2 or greater and/or if the calcium, magnesium, and/or phosphate are grade 3 or higher, an EKG must be performed and appropriate action taken based on the results.

Treatment may be delayed for a maximum of 2 weeks for toxicities. In case toxicities do not resolve as stated, the patient will not receive further therapy on this protocol and will be followed for resolution of toxicities. Start of next cycle may be delayed for up to 1 week to accommodate scheduling conflicts. Dose modifications are intended for within-cycle and start-of-next-cycle changes.

A maximum of 2 dose reductions will be allowed before patient is taken off treatment. Patients who require a dose reduction will not have the dose re-escalated. For patients who had one dose reduction without significant change in their toxicities (i.e., fatigue), they could be dose reduced to 4 days of the same dose level instead of dropping to the next lower dose level.

Patients will be carefully monitored for evidence of liver toxicity and toxicity will be graded per CTCAE criteria ([Section 7.2](#)). For patients who develop grade 3 LFT abnormalities, study drugs will be held and the benefits and risks of continuing treatment on a reduced dose will be discussed with the patient by the study team.

6.1 Dose Reduction

Grade 2 Drug-related toxicities: No changes will be made to the dose of TRC102/TMZ for Grade 2 toxicities.

Grade 3-4 Drug-related non-hematologic toxicities (except alopecia): Doses of TRC102/TMZ will be held until toxicities recover to \leq Grade 1 prior to re-initiating treatment at the lower dose level. Electrolyte abnormalities will not require dose reduction if resolution to Grade 2 or less is documented. Dose modifications for nausea, vomiting, and diarrhea will be made only if they are refractory to treatment (See [Section 5.2](#)).

Grade 3-4 Drug-related thrombocytopenia: Dose of TRC102/TMZ will be held until it has resolved to \leq Grade 1 prior to re-initiating treatment at the lower dose level.

Grade 3-4 Drug-related neutropenia: Dose of TRC102/TMZ will be held until it has resolved to \leq Grade 2 prior to re-initiating treatment at the lower dose level.

A drop in Hgb ≥ 3.0 g/dL over one week that results in grade 3 anemia: Dose of TRC102/TMZ will be held until it has resolved to \leq Grade 2 prior to re-initiating treatment at the lower dose level.

Any grade lymphopenia, leucopenia in the absence of at least grade 3 neutropenia: Dose of TRC102/TMZ will not be held or modified.

Definition of Complete Course: A cycle is defined as 28 days, with D1 starting the first day of TRC102/TMZ administration. If a patient receives 90% of scheduled treatments of TRC102/TMZ and remains in the study until D28, the patient will be considered to have completed a cycle of therapy. Patients who do not complete a cycle of therapy for reasons other than toxicity will be replaced. Patients who do not complete one cycle of therapy due to toxicity will not be replaced. All patients should have completed one cycle of therapy (unless removed from the study due to toxicity), at which point they will be evaluable.

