5. TREATMENT PLAN

Phase I: This is an open-label Phase I trial evaluating the combination of oral TRC102 with oral TMZ, in 28-day cycles. The starting dose of TRC102 is based on the safety information from the trial of IV TRC102 combined with TMZ. The study will follow a 3+3 design: dose will be escalated in cohorts of 3 patients with the individual dose of TRC102 and TMZ increased in successive dose levels as outlined in the dose escalation table below. Once the MTD is established, up to 15 additional patients will be enrolled at the MTD (expansion phase) to further define the dose and evaluate PK and PD at this dose level.

Phase II: Patients with a body surface area (BSA) of $\geq 1.6 \text{ m}^2$ will be started on 125 mg TRC 102 and 150 mg/m² Temozolomide orally on days 1-5 of each 28-day cycle (DL6). Patients with a BSA of $< 1.6 \text{ m}^2$ will be started on 100 mg TRC 102 and 150 mg/m² Temozolomide orally on days 1-5 of each 28-day cycle (DL5). There will be no dose escalation for patients on the Phase II portion of the study; appropriate dose modifications are described in [Section 6](#). Up to 75 patients will be accrued to this part of the study.

History and physical examination can be done up to 8 days before start of a new cycle. Patients will be examined at baseline for the first cycle then at the start of every cycle for the remainder of the study (up to 3 days before start of a new cycle). The start of the next cycle may be delayed for up to 1 week to accommodate scheduling conflicts.

Labs (CBC with differential; serum chemistries) will be performed (+/- 2 days) as follows: every week up to week 3 for cycle 1. Starting with cycle 2, labs (CBC with differential; serum chemistries) will only be performed before the start of each cycle (laboratory evaluation may be performed up to 7 days prior to scheduled date to accommodate scheduling conflicts and patient convenience). If clinically indicated, labs may be obtained more frequently.

Blood for erythrocyte analysis (optional) will be collected on cycle 1 days 7, 14, and 21 (+/- 2 days) as described in [Appendix F](#).

CT scans will be performed at baseline, and repeat scans will be performed every 2 cycles (every 3 cycles for patients on study more than one year).

Phase I Dose Escalation Schedule (28-day cycle)		
Dose Level	TRC 102 orally	TMZ orally
Level -2	25 mg once daily D1-5	75 mg/m ² once daily D1-5
Level -1	25 mg once daily D1-5	100 mg/m ² once daily D1-5

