APPENDIX F: ERYTHROCYTE ANALYSIS

Please note: As of Amendment R (5/12/18), we will no longer perform this analysis of the mechanisms of extravascular hemolysis.

Blood will be collected for the analysis below in collaboration with the hematology attending consult team. These studies are optional. Blood volumes may be changed at the PI/consult team's discretion. Additional studies (Folate, Vitamin B12, Erythropoietin, TSH) may be done as clinically indicated based on baseline Hgb values.

Blood collection tubes, volumes, and service for each test can be found at the Dept. of Transfusion Medicine's Test Guide: <http://cclnprod.cc.nih.gov/dlm/testguide.nsf/>

When patients develop Hgb level decrement of more than 2 g/dL of baseline during cycle follow-up, contact the hematology consult team for official consultation ([name], [contact]; [contact]); the hematology attending consult team will develop a reference guide/SOP. The hematology consult team will order necessary labs, review the peripheral blood smear, and obtain systematic relevant hematological history at the time of consultation.

Laboratory testing/ timing

1) Baseline (within 72 hours prior to enrollment)

- CBC with WBC differential
- Reticulocyte count
- Peripheral blood smear evaluation
- LDH
- LFTs
- Haptoglobin
- Ferritin, iron study
- DAT (Direct Coombs test)
- Renal function
- Urinalysis with microscopy, urine urobilinogen
- G6PD
- Spleen size evaluation (if CT is done recently per protocol, there is no need to repeat. If not, then US spleen)
- Osmotic fragility test
- RBC enzyme evaluation
- Methemoglobin, venous

2) C1D7 +/- 2 days

- CBC with diff
- Reticulocyte count
- Peripheral blood smear
- LDH

- LFTs
- Haptoglobin
- DAT
- Ferritin, iron study
- Urinalysis with microscopy, urine urobilinogen
- RBC enzyme evaluation
- Osmotic fragility test
- Methemoglobin, venous

3) C1D14 +/- 2 days, C1D21 +/- 2 days

- CBC with diff
- Reticulocyte count
- Peripheral blood smear
- LDH
- LFTs
- Haptoglobin
- DAT
- Urinalysis with microscopy, urine urobilinogen

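### From cycle 2 the scheduled blood counts cannot show the one-week hemoglobin fall that Section 6.1 requires before the dose is lowered for anemia, and grade 4 anemia is not named

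*Combined protocol and SAP*

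**What the plan says.** - **Anemia, Section 6.1.** The only entry is "A drop in Hgb ≥ 3.0 g/dL over one week that results in grade 3 anemia". Drug is then held to grade 2 or lower and restarted at the lower dose level.
- **Neutropenia and thrombocytopenia, Section 6.1.** The neutropenia entry begins "Grade 3-4 Drug-related neutropenia: Dose of TRC102/TMZ will be held until it has resolved to" grade 2 or lower, followed by the lower dose level. Thrombocytopenia is handled the same way with grade 1 as the bar. Neither depends on speed of fall.
- **Restarting, Section 6.** At least possibly related anemia must be at or below "Grade 2 for neutropenia and anemia prior to resuming therapy". No dose level is attached, and a transfused value is not excluded. Also: "Treatment may be delayed for a maximum of 2 weeks for toxicities", and "A maximum of 2 dose reductions will be allowed before patient is taken off treatment". A reduced dose is not raised again.
- **DLT, Section 5.2.1.5 (Phase I).** A hemoglobin drop of at least 3.0 g/dL within one week is dose-limiting. The hematologic list has no criterion for grade 3-4 anemia alone.
- **Blood counts, Section 5.** "Starting with cycle 2, labs (CBC with differential; serum chemistries) will only be performed before the start of each cycle", with draws allowed up to 7 days early and extra labs if clinically indicated. Section 5 gives weekly cycle 1 CBCs up to week 3 without naming a phase; footnote c of the Section 10 calendar limits them to Phase I.
- **Erythrocyte bloods.** "Blood for erythrocyte analysis (optional) will be collected on cycle 1 days 7, 14, and 21", but Appendix F states that "we will no longer perform this analysis of the mechanisms of extravascular hemolysis".
- **Transfusion.** Section 5.3.4 recommends it below 8 g/dL. Section 3.1.7 bars it within 4 days before enrollment; no parallel rule covers re-treatment.
- **Known toxicity, Section 2.5.** Hemolytic anemia was dose-limiting in this trial, with the MTD exceeded at dose level 8.

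**The concern.** A grade can be read from one CBC. The 6.1 anemia trigger needs two CBCs no more than a week apart. Once the weekly cycle 1 counts end, the calendar provides no such pair, so whether a reduction is mandatory depends on whether someone happened to draw extra blood.

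At stake is re-exposure in Phase II (accrual ceiling 75) to an unchanged TRC102 dose after severe related anemia. Dose reduction is the relevant tool here: from dose level 6 or 5, each of the next two lower levels cuts TRC102 and leaves TMZ at 150 mg/m². Section 7.1 lists anemia as possibly related to TRC102, while it places neutrophil and platelet decreases among events with insufficient evidence of a TRC102 cause. As written, a single grade 3 neutrophil or platelet count forces a TRC102 cut; a single grade 3 or 4 hemoglobin does not.

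**Working it through.** The plan states no figure on this point, so the check compares the one-week interval the trigger needs with the intervals the schedule supplies.

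**1. Gap between scheduled CBCs from cycle 2.** Inputs: 28-day cycle; draw 0 to 7 days early (Section 5).
- Minimum: 28 − 7 = 21 days. Maximum: 28 + 7 = 35 days.
- Adding the ±1 day cycle window and a scheduling delay of 0 to 7 days: 27 − 7 = 20 to 29 + 7 + 7 = 43 days.
- Adding the ±2 day lab window as well (the loosest reading): 16 to 47 days.
- Scheduled pairs within 7 days: 0 on every reading.

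**2. Phase II cycle 1, if footnote c governs.** Baseline is 0 to 8 days before day 1 and the pre-cycle-2 draw 0 to 7 days early: 28 − 7 = 21 to 28 + 8 = 36 days. If Section 5 governs, weekly counts exist and the gap starts only at cycle 2.

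**3. What other labs can show.**
- The Section 10 repeat, within 48 hours before the next cycle, applies only to a deteriorating patient. An early pre-cycle draw can fall on day 29 − 7 = 22 and the repeat on days 27 to 29, so the pair spans at most 7 days. It covers only days 22 to 29, starting 22 − 5 = 17 days after the last dose.
- One unscheduled CBC lies within a week of the draw opening the cycle up to day 1 + 7 = 8 if that draw was on day 1, or only day 1 if it was 7 days early. It lies within a week of the draw closing the cycle from day 29 − 7 = 22 if that draw is on time, or day 22 − 7 = 15 if it is 7 days early. With on-time draws, a fall within days 9 to 21 needs two unscheduled CBCs.

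**4. Hemoglobin arithmetic.** Assumption: grade 3 begins below 8.0 g/dL (range 7.5 to 8.5; the documents do not define it).
- Starting value below which grade 3 can be reached without a 3.0 g/dL fall: 8.0 + 3.0 = 11.0 g/dL (10.5 to 11.5).
- From the entry floor of 10.0 to 7.5 in one week: fall 2.5, grade 3, no reduction required.
- Assuming grade 2 is 8.0 to 9.9 g/dL, a patient restarted there meets the trigger only at 8.0 − 3.0 = 5.0 to 9.9 − 3.0 = 6.9 g/dL, reached within a week.

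**5. Illustrative cases under the present rule and under the fix.**

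| Pre-cycle Hgb | Next pre-cycle Hgb, 28 days later | Fall | Required by 6.1 now | Required under the fix |
|---|---|---|---|---|
| 11.5 | 7.5 | 4.0 | No (no one-week pair) | Yes |
| 10.0 | 7.5 | 2.5 | No | No (left to the sponsor) |

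Any drug-related grade 4 value would require reduction under the fix, whatever the fall.

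**The case against.** The strongest defence is that a speed-based rule looks deliberate. It matches the DLT criterion used to choose the dose, and it targets acute hemolysis rather than slow anemia in pretreated patients. Section 2.5 calls the anemia in the pemetrexed study reversible and manageable with supportive care, and reports no cumulative hematologic toxicity in the preclinical work. Phase II doses are below dose level 8. Section 6 bars dosing while related anemia exceeds grade 2 and ends treatment if it does not resolve within the 2-week limit. Clinically indicated labs, expedited reporting of serious events, transfusion reporting in cycles 1 to 3 and investigator discretion to stop add protection. Appendix F also calls for a hematology consult after a fall of more than 2 g/dL from baseline, though its status since Amendment R is unclear.

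Much of this stands. It answers three stronger readings that a reader might infer:

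- *That all grade 3 anemia must force a reduction, as neutropenia does.* The documents do not support this as a correction. The DLT definition is itself speed-based, and permanent reduction for slow, recoverable anemia is a trade-off.
- *That the protocol directs a same-dose restart or dosing through grade 3.* It does neither: it permits the former, forbids the latter, and does not prohibit a voluntary reduction.
- *That Phase II exposure nearly equals the pemetrexed regimen with 50% grade 3 anemia (n=6).* Per cycle, 125/1.6 × 5 = 391 and 100 × 4 = 400 mg/m² look alike. Those combination cycles were 3 weeks, however: 391/4 = 98 against 400/3 = 133 mg/m² per week, about 27% lower, and 78 at BSA 2.0. The partner drug also differs.

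What the defence does not answer is the mismatch between trigger and schedule. If the speed test is deliberate, it should be observable. None of the safeguards listed requires a lower dose once anemia has recovered or been transfused to grade 2.

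**Conclusion.** The point holds as a mismatch between the 6.1 anemia trigger and the CBC calendar, plus silence on grade 4. On nominal cycles no scheduled pair from cycle 2 onward is closer than 21 days (16 on the loosest reading), against the 7 days needed. The same may apply to Phase II cycle 1, depending on whether Section 5 or footnote c governs.

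The hemoglobin examples rest on the assumed grade cut-offs; the timing result does not. The number of patients affected is unknown: no Phase II anemia rate is given, and the content under the current-status heading in Section 2.3 was not available. That the trigger was carried over from the Phase I DLT without adjusting for sparser counts is a reasonable inference, not something the protocol states.

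This is a worthwhile, inexpensive safety improvement. It is not evidence that the chosen dose is unsafe or that the response-rate design is compromised.

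**What to change.** Amend the 6.1 anemia entry so that TRC102/TMZ is held to grade 2 or better and re-initiated at the lower dose level after either:

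- (a) any drug-related grade 4 anemia; or
- (b) drug-related grade 3 anemia, transfused or not, with a hemoglobin fall of at least 3.0 g/dL over one week or, when no CBC from the prior week exists, from the most recent earlier CBC.

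This keeps the sponsor's threshold and makes it readable from counts already scheduled. Extending the reduction to all drug-related grade 3 anemia regardless of fall is an option for the sponsor, not a required correction.

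**Cost.** One clause and no new labs. Some patients will have additional permanent TRC102 reductions, since re-escalation is not allowed. Some may reach the two-reduction limit sooner, with possible loss of dose intensity in the response-rate cohorts. By dose level, two reductions take TRC102 from 125 to 75 mg (1 − 75/125 = 40%) from level 6, or from 100 to 50 mg (50%) from level 5, with TMZ unchanged. The 4-day alternative in Section 6 would lower both drugs.

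**Limit.** Anemia that appears and resolves, or is transfused, between pre-cycle draws would still need an unscheduled CBC to be seen.
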